When in the direct contact with even a small amount of blood, the compound forms an occlusive seal through simultaneous iron-mediated agglomeration of blood solids/proteins and rapid dehydration of the blood. Seal formation is independent of the clotting cascade, facilitating sealing regardless of anticoagulation / antiplatelet status of the patient. Following cessation of pressure being applied to the site, the remnants of StatSeal form what resemble a 'scab', and remains in place for 24 hours, covered with a band-aid or Tegaderm patch.

In clinical testing using a protocol refined at the University of Miami Miller School of Medicine, the use of this compound in conjunction with commercially available hemostasis bands has demonstrated the potential to significantly shorten the time required to achieve hemostasis^{11,12}. Further, these results demonstrated the ability to achieve hemostasis using StatSeal with similar, or fewer complications when compared to standard methods, and did so regardless of the patient's anticoagulation status.

INDICATION FOR USE

StatSeal Advanced is a commercially available product in the United States, and is indicated for use on patients in whom the radial artery has been used to gain vascular access for a cardiovascular procedure.

DEVICE STORAGE AND ACCOUNTABILITY

StatSeal Advanced is provided in a sterile, foil pouch to protect it from humidity / moisture. As with most medical products, it should be stored in a cool, dry, secure environment. StatSeal Advance will be provided at no charge by the manufacturer for use in the study.

Damaged devices will be returned to the manufacturer (Biolife, LLC, Sarasota,FL). All unused devices may be retained by the site for continued use, if they so choose.

III. STUDY OBJECTIVE(S)

The primary objectives of this study are to evaluate the performance of StatSeal Advanced used in conjunction with the TR Band (SSA) as compared to the TR Band without SSA (TRB) relative to:

1. the incidence of peri-procedural radial artery occlusion (RAO) at discharge or 24 hours, whichever occurs first, and;
2. the Time to Hemostasis (TTH)

HMS is defined as the Hemostasis Management System employed based on which group the patient is randomized to (either SSA or TRB).

Radial Artery Occlusion is defined as the absence of flow to the hand based upon plethysmography – pulse oximetry (Pleth-Ox) performed using the Barbeau scale.

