Time to Hemostasis (TTH) is defined as the time period required to achieve hemostasis, more specifically the time during which the subject is wearing the HMS system and the system is active, e.g. applying compressive force to the access site. For clarity, the time period that a HMS is left on the wrist while totally deflated is not considered as part of the TTH time.

IV. STUDY DESIGN AND METHODOLOGY

STUDY DESIGN

This study is a physician initiated, prospective, observational, two arm, randomized study to be performed at up to four experienced 'Radial First' centers. A minimum of 120 patients having undergone successful radial catheterization will be enrolled in the study, 60 in each arm.

Enrollment will continue at each site on discretion of the investigators until each center enrolls a minimum of 30 patients, or a maximum of 180 patients are enrolled. Clinicians will perform the catheterization in accordance with local standard practice, with a minimum of 5,000 units of unfractionated heparin for anticoagulation.

STUDY METHODS:

Patient Selection Criteria Study subjects will be identified in the catheterization laboratory holding area and asked to sign the informed consent prior to their catheterization procedure before the administration of sedative agents.

Inclusion Criteria:

- Patient undergoing diagnostic angiography or PCI via the radial artery
- Patients with a Barbeau test prior to the procedure showing pattern A,B,or C.

Exclusion Criteria:

Candidates for this study will be excluded if any **one** of the following criteria is true.

- Use of a radial sheath larger than 6 Fr (a 7Fr-in-6 Glidesheath Slender[®] is allowed).
- Use of an anticoagulant other than unfractionated heparin or bivalirudin.

- Any anticipated need for continued anticoagulation post-catheterization. Glycoprotein inhibitors are acceptable.
- Any active treatment with oral anticoagulants continued during course of procedure.
- Presence of arteriovenous dialysis fistula in the ipsilateral arm.
- Any physical deformity or trauma / injury of either wrist that would prevent proper placement or function of the hemostasis band.
- Raynaud's syndrome or known peripheral vascular disease of the forearm.
- Mental incompetence or inability to follow the instructions to complete the study.
- History or presence of Radial Artery Occlusion.
- Barbeau test showing Pattern D.
- Patients undergoing catheterization from the femoral or ulnar artery approach.

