Diabetes: Hgb A1C >6.5% or active medical treatment for diabetes.

Hypercholesterolemia: LDL >130 or on treatment with antilipemic agents.

Hypertension: >140/80 or on medical treatment for hypertension.

Diagnostic procedure: Involving diagnostic catheters only.

Interventional procedure: Involving an interventional wire and therapeutic ACT typically >200, including for fractional flow reserve measurement where a stent is not placed.

Single wall puncture: Use of micropuncture wire and anterior wall puncture only.

Double wall puncture: Use of double wall puncture and sheath withdrawal technique.

Number of forward attempts: Number of forward advancements of the needle required to obtain access (not number of separate punctures of skin).

Procedure Start Time: Time when lidocaine is administered, prior to first puncture attempt.

Procedure End Time: Time when sheath is removed.

Test methodology:

All Pleth-ox testing will be done by qualified personnel with results classified according to Barbeau test pattern classifications. [Barbeau, et al. *Evaluation of ulnopalmar arterial arches with pulse oximetry and plethysmography; comparison with the Allen's test in 1010 patients. Am Heart Journal; 2004; 147:489-493*]

At the start of the TRA procedure, prior to radial artery cannulation, a baseline Pleth-ox exam will be performed for all patients and recorded on the CRF. Ulnar compression will be applied to confirm that the radial artery is patent. Patients with a type D pattern exam will be excluded from the study.

At the conclusion of a successful transradial procedure, the patient will be randomized to either SSA or TRB, each device applied per protocol & IFU.

Following placement of the HMS system, Pleth-Ox exams will be performed at the following time points with results recorded in the CRFs.

- Within 5 minutes of initial HMS placement
- In the SSA (StatSeal Advanced) group, within 5 minutes of the first partial deflation (20 minutes after initial placement).
- Within 5 minutes of full deflation of the HMS in both groups
- Within 30' of discharge or 24 hours post procedure (\pm 1 hour), whichever occurs first.

VI. STUDY STATISTICAL PLAN:

This is a physician initiated, prospective, randomized, two-arm study, to be conducted at up to four experienced 'Radial First' centers with the principal investigator having a (minimum) ten case experience using StatSeal Advanced.

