The sample size of 120 patients is estimated to have 90% power to detect an average difference in time to removal of the TR band of 60 minutes between the SSA and TRB groups, using a relatively large standard deviation of 100 minutes and a two-sided alpha of 0.05.

Descriptive summary statistics will be presented for all study variables. Continuous variables will be displayed as means with standard deviations and medians with 75th and 25th percentiles. Categorical variables will be summarized as frequencies with their respective percentages with two-sided 95% exact confidence intervals of the percentages. Statistical comparisons for continuous variables will be performed using the Student's t test or Mann-Whitney U test, as appropriate. Comparisons for categorical variables will be performed using the Chi square test or Fisher exact test, as appropriate. A two-sided P value of 0.05 will be considered statistically significant.

Categorical variables will include, but are not limited to:

- Percent of patients in each arm with total TTH of 60 minutes or less.
- Percent of patients in each arm with TTH of 40 minutes or less without complication.
- The percentage of patients in each arm with bleeding, oozing or hematoma during TTH, further delineated by the EASY bleeding and hematoma classification attached.
- Percent of patients in each arm with RAO at each /all follow-up points.
- Percent of patients in each arm with radial patency as tested with Pleth-ox at each designated test time point.

Primary Efficacy Outcomes:

In each arm the:

- Total Time to Hemostasis (TTH), defined as the total time the HMS applies compressive force until successful hemostasis is achieved without complication.

Secondary Efficacy Outcomes:

In each arm the:

- Percent of patients free from radial artery occlusion at discharge or at 24 hours, whichever occurs first.
- Percent of patients with Barbeau test patterns A,B,C,D at initial application of the HMS
- Percent of SSA patients with Barbeau test patterns A,B,C,D after 20' of HMS time.
- Percent of patients with Barbeau test patterns A,B,C,D at full deflation of the HMS. (40' for SSA group; per protocol in the TRB group)
- Percent of patients with Barbeau test patterns A,B,C,D at discharge or at 24 hours, whichever occurs first.
- Percent of patients in whom successful hemostasis is achieved in one hour or less.

Primary Safety Outcome:

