A PROSPECTIVE RANDOMIZED STUDY COMPARING THE INCIDENCE OF RADIAL ARTERY OCCLUSION (RAO) AND THE TIME TO HEMOSTASIS (TTH) WHEN USING A HEMOSTASIS BAND ALONE AND IN CONJUNCTION WITH A DISC COMPRISED OF POTASSIUM FERRATE (STATSEAL ADVANCED) FOLLOWING TRANSRADIAL CATHETERIZATION. Study Sponsor: A Physician Initiated Study

Principal Investigator: [name], MPA

Cardiology Division Veterans Medical Center Long Beach

Statistical Analysis

Continuous data are presented as mean \pm standard deviation and as median [interquartile range], and compared using unpaired t-test and Mann-Whitney U-test, respectively. Discrete data are presented as frequencies with their respective percentages and compared using Fisher's exact test. Outcome data were analyzed on an intention-to-treat basis. Two-tailed tests of significance are reported and p values < 0.05 were considered statistically significant. Univariate logistic regression was performed using all baseline patient and procedural variables available to predict the secondary outcome of hematoma formation. Variables that were significant in univariate analysis at $p<0.25$ were retained and entered into a multivariate model with a threshold of $p<0.05$ being considered as significant. Statistical analyses were performed using the SPSS statistical software program (SPSS version 16.0.2, Chicago, IL).

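### The planned comparison of Barbeau pattern at discharge/24 h ignores both the order of the patterns and the baseline pattern already recorded, so it gives up power to detect shifts within A–C

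*Protocol*

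**What the plan says.** Entry (Protocol, Section IV, Inclusion Criteria) admits "Patients with a Barbeau test prior to the procedure showing pattern A,B,or C". Section V, Test methodology, adds "Patients with a type D pattern exam will be excluded from the study". The same section says that before cannulation "a baseline Pleth-ox exam will be performed for all patients and recorded on the CRF". Randomization comes later, at the end of a successful procedure, so this is a true pre-randomization baseline.

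Section VI lists as a secondary efficacy outcome "Percent of patients with Barbeau test patterns A,B,C,D at discharge or at 24 hours, whichever occurs first", with matching items at initial application and at full deflation. Freedom from RAO at discharge/24 h is a separate item in the same list.

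No test is attached to the pattern outcome itself. The general rule in Section VI is "Comparisons for categorical variables will be performed using the Chi square test or Fisher exact test, as appropriate". The SAP says "Discrete data are presented as frequencies with their respective percentages and compared using Fisher's exact test". Neither document gives an ordinal method, a change from baseline, a shift table or a baseline adjustment for Barbeau pattern. The only model that uses baseline variables is the SAP's logistic regression for hematoma.

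**The concern.** The outcome uses a four-level scale, and patients can start on three of the four levels. A chi-square or Fisher test on the 2×4 table of arm by discharge pattern sees only where patients end. It cannot separate a patient who entered at A and left at C from one who was at C throughout. Variation in entry pattern therefore enters the comparison as noise, although the value that would remove it is already on the CRF. The test also treats the four patterns as labels without order.

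This matters because the sample size rests on time to band removal, and frank occlusion is uncommon: the protocol's background puts it at about 5–10%. The graded pattern is where a smaller difference in flow between arms could show.

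**Working it through.** **The plan's own figure.** The only sample-size statement concerns time to band removal: difference 60 min, SD 100 min, two-sided alpha 0.05, 90% power.

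- Normal approximation: n per arm = 2 × (1.960 + 1.282)² × 100² / 60² = 58.4, so 59 per arm (118 in total).
- The t-test version needs 59.4, so 60 per arm, or 120.

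The stated 120 reproduces. It has no bearing on Barbeau pattern, for which no figure is given.

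**Why RAO alone shows little at this size.** Take 10% versus 5% (assumed, from the two ends of the background range) with 60 per arm. The null SE is √(2 × 0.075 × 0.925 / 60) = 0.0481 and the alternative SE is √((0.10 × 0.90 + 0.05 × 0.95) / 60) = 0.0479. Power = Φ((0.05 − 1.96 × 0.0481) / 0.0479) = Φ(−0.92) = 18%.

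**Chance difference in entry pattern.** For a pattern held by a proportion p at entry, the 95% range of the between-arm difference is ±1.96 × √(2p(1 − p)/60). This is ±10.7 points at p = 10%, ±14.3 at 20% and ±17.9 at 50%.

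**Simulation of the pattern comparison.** The documents give no entry mix, worsening rate or reading error, so all of these are assumptions. The planned test is represented by a Pearson chi-square on the 2×4 table. The alternative is the van Elteren test: within each baseline pattern s, take the rank sum minus its expectation n₁(N + 1)/2, weight by 1/(N + 1), sum over s, and divide by the square root of the summed weighted tie-corrected variance.

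Set 1: 60 per arm, worsening by one or two levels; reading noise moves 15% of readings up and 15% down one level.

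| Assumed worsening, TRB vs SSA | Reading noise | Planned 2×4 test | Stratified by baseline |
|---|---|---|---|
| 30% vs 10% | none | about 27–34% | about 79% |
| 30% vs 10% | yes | 20–24% | 47–48% |
| 20% vs 10% | none | about 10% | 33–35% |
| 20% vs 10% | yes | about 7% | 14–17% |

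Set 2: different rates, four-fifths of worsening by one level, no noise, entry mixes A/B/C from 90/8/2 to 34/33/33.

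- 35% vs 15%, 60 per arm: unordered 19–39%; ordered without baseline 22–54%; ordered and stratified by baseline 69–72%; simple worsened yes/no 71–73%.
- 35% vs 15%, 90 per arm (the 180 maximum): unordered 30–58%; stratified 87–89%.
- 25% vs 15%, 60 per arm: unordered 8–12%; stratified 26–27%.
- No true difference: type I error 3.3–6.0% across all methods, that is, about 5%.

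**Which part of the change does the work.** At 30% vs 10%, entry mix 50/30/20, no noise: unordered about 27%, ordered without baseline about 33%, stratified about 79%. Using baseline is the main gain. Order without baseline can even cost power: if all worsening goes straight to D (assumed 10% vs 2%), the 2×4 test has 26–27%, an unstratified Wilcoxon 12–21% and the stratified Wilcoxon 44–47%.

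**When baseline does not help.** With discharge pattern unrelated to baseline (same rates and mix), power is 27% unordered, 31% ordered and 31% stratified. Stratifying then adds nothing over order alone, and costs nothing.

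**The case against.** - **Is deterioration hidden?** A reader might infer that occlusion goes unseen. It does not. Nobody enters at D, so every D at discharge is new, and RAO is analysed separately. Partial loss within A–C is not a stated objective. This confines the point to shifts within A–C.
- **Is the comparison biased?** A reader might also infer that a chance imbalance at entry would pass for a device effect more often than it should. Baseline precedes randomization and type I error stays near 5%, so chance imbalance is already within the error rate. The loss is of efficiency.
- **Is the order given?** RAO is defined as "absence of flow to the hand based upon plethysmography – pulse oximetry (Pleth-Ox) performed using the Barbeau scale", and the word scale together with the exclusion of D implies an order. Neither document writes out A<B<C<D, or says that moving from A to C means radial flow has been lost. The plan should state the order.
- **Are the exams comparable?** At baseline, "Ulnar compression will be applied to confirm that the radial artery is patent". The later exams carry no such description. If the manoeuvre differs, worsening has no clear meaning and the gain from baseline may disappear. This stands as a condition on the fix.
- **Is the size of the gain chosen?** It depends on assumed rates. At 20% vs 10% or 25% vs 15% even the better analysis would usually miss the difference.
- **Is a test planned at all?** The 2×4 comparison follows from a general rule, and the outcome could be meant as description only. In that case a shift table is still the more informative description.
- **Is baseline never used?** That would be too strong: the SAP's hematoma model draws on all available baseline variables. It is unused for the Barbeau comparison.

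**Conclusion.** The point holds as a loss of power in one secondary outcome. Under the general rule, discharge/24 h Barbeau pattern would be compared without its order and without a baseline value recorded for every patient. In every scenario in which discharge pattern depends on baseline, the stratified ordered test had more power, with type I error near 5%. The size is uncertain: from roughly 27–34% up to 79% in the most favourable Set 1 case, and from about 7% to 14–17% in the least favourable. These figures rest on assumed entry mixes, worsening rates and reading noise, and on the same exam being done at both times. The documents do not support reading this as bias, as concealed occlusion, or as a threat to the TTH result.

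**What to change.** In Protocol Section VI and the SAP:

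1. Keep the A–D percentages by arm as description.
2. State the order A<B<C<D, and state that the same Pleth-Ox manoeuvre is used at baseline and at the later exams.
3. Compare the discharge/24 h pattern between arms with a Wilcoxon test stratified by baseline pattern (van Elteren), or a proportional-odds model with baseline pattern as covariate. Name one of the two in advance, apply it to the full-deflation pattern as well, and label both analyses secondary.
4. Add a baseline-by-discharge shift table for each arm.

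The cost is wording and a short analysis program. Baseline and later patterns are already recorded on the CRF, so no patients or assessments are added. If the manoeuvre turns out to differ between exams, the shift table and the term worsening should not be used until that is resolved. The primary TTH analysis, the RAO analysis and the sample size stay as they are.

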Appendix 1: Sample Informed Consent

Appendix 2: CRF's

A PROSPECTIVE RANDOMIZED STUDY COMPARING THE INCIDENCE OF RADIAL ARTERY OCCLUSION (RAO) AND THE TIME TO HEMOSTASIS (TTH) WHEN USING A HEMOSTASIS BAND ALONE AND IN CONJUNCTION WITH A DISC COMPRISED OF POTASSIUM FERRATE (STATSEAL ADVANCED) FOLLOWING TRANSRADIAL CATHETERIZATION. Study Sponsor: A Physician Initiated Study

Principal Investigator: [name], MPA

Cardiology Division Veterans Medical Center Long Beach

Statistical Analysis

Continuous data are presented as mean \pm standard deviation and as median [interquartile range], and compared using unpaired t-test and Mann-Whitney U-test, respectively. Discrete data are presented as frequencies with their respective percentages and compared using Fisher's exact test. Outcome data were analyzed on an intention-to-treat basis. Two-tailed tests of significance are reported and p values < 0.05 were considered statistically significant. Univariate logistic regression was performed using all baseline patient and procedural variables available to predict the secondary outcome of hematoma formation. Variables that were significant in univariate analysis at $p<0.25$ were retained and entered into a multivariate model with a threshold of $p<0.05$ being considered as significant. Statistical analyses were performed using the SPSS statistical software program (SPSS version 16.0.2, Chicago, IL).

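### Fisher's exact test, fixed by the SAP for all discrete outcomes, is valid but conservative for RAO at 60 per arm; Boschloo's exact test would recover some power at the same 5% guarantee

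*SAP*

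**What the plan says.** The SAP (Statistical Analysis) states: "Discrete data are presented as frequencies with their respective percentages and compared using Fisher's exact test". Its significance rule is: "Two-tailed tests of significance are reported and p values < 0.05 were considered statistically significant".

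Protocol section VI is wider on the test, "Comparisons for categorical variables will be performed using the Chi square test or Fisher exact test, as appropriate", and the same on the level: "A two-sided P value of 0.05 will be considered statistically significant". The SAP therefore narrows the protocol's choice to Fisher's test alone.

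Protocol section III lists "the incidence of peri-procedural radial artery occlusion (RAO) at discharge or 24 hours, whichever occurs first" as the first of two primary objectives. Section VI makes time to hemostasis the only primary efficacy outcome and places freedom from RAO among the secondary ones.

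On size, section IV says: "A minimum of 120 patients having undergone successful radial catheterization will be enrolled in the study, 60 in each arm". Enrollment may continue until each center reaches its minimum "or a maximum of 180 patients are enrolled". The only power statement, "The sample size of 120 patients is estimated to have 90% power", concerns time to band removal. Neither document gives an RAO effect size or RAO power.

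**The concern.** RAO is a yes/no outcome at a low rate. Section I of the protocol gives a background of roughly 5-10%, and under 5% for late occlusion with patent hemostasis. With few events, Fisher's p value moves in large steps, and the test often cannot come near its nominal level. At 60 per arm it cannot reach p<0.05 with fewer than six events in total, even if all fall in one arm.

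A real reduction in RAO, access-site complications or hematoma could then be missed although another exact test with the same guarantee would have detected it. This matters more because the sample size was not set for RAO.

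**Working it through.** **The plan's own figure.** The inputs in protocol section VI are a 60-minute difference, SD 100, two-sided alpha 0.05 and power 90%. The normal formula gives n per arm = 2 × (1.960 + 1.282)² × (100/60)² = 2 × 10.51 × 2.778 = 58.4, so 59. With the noncentral t distribution, 60 per arm has 90.3% power. The stated 120 reproduces, but it says nothing about RAO.

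**Inputs for RAO.** 60 per arm (minimum) and 90 per arm (maximum of 180, if split 1:1) come from section IV. Two-sided 0.05 comes from the SAP. Control RAO of 5-10% comes from section I. The SSA rates are assumptions.

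**Method.** Every possible two-by-two table (61 × 61, or 91 × 91) was enumerated under two independent binomials. Fisher rejects where its two-sided p is below 0.05. Boschloo uses the Fisher p value as its statistic and takes the largest cut-off whose rejection probability, maximised over all common event rates, does not exceed 0.05. That cut-off is a Fisher p of 0.0665 at 60 per arm and 0.0669 at 90 per arm. Both exceed 0.05, so Boschloo rejects every table that Fisher rejects.

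**Actual size, 60 per arm**

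| Common event rate | Fisher | Boschloo |
|---|---|---|
| 3% | 0.3% | 1.2% |
| 5% | 1.05% | 2.7% |
| 7.5% | 1.7% | 3.3% |
| 10% | 2.2% | 3.4% |
| 20% | 2.8% | 4.0% |
| 50% | 3.5% | 4.4% |
| Maximum over all rates | 3.5% | 4.9% |

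**Hand check.** For 5 v 0, Fisher's p = 2 × (60·59·58·57·56)/(120·119·118·117·116) = 2 × 0.0287 = 0.057, not significant. For 6 v 0, p = 0.027. Against zero SSA events, Fisher therefore needs 6 control events and Boschloo needs 5. If the true SSA rate is 0%, power is simply the chance of that many control events among 60. At a 10% control rate, P(X ≥ 6) = 56.3% and P(X ≥ 5) = 72.9%. At 5% the two figures are 7.9% and 18.0%.

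**Power (SSA rates assumed)**

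| Control v SSA | 60/arm: Fisher → Boschloo | Gain, points | 90/arm: Fisher → Boschloo | Gain, points |
|---|---|---|---|---|
| 10% v 0% | 56.3 → 72.9 | 16.6 | 89.7 → 95.3 | 5.6 |
| 10% v 1% | 39.8 → 54.4 | 14.6 | 70.0 → 79.0 | 9.0 |
| 10% v 2% | 27.7 → 39.5 | 11.8 | 51.9 → 60.7 | 8.8 |
| 10% v 5% | 8.8 → 13.4 | 4.6 | 17.1 → 20.9 | 3.8 |
| 7.5% v 0% | 29.4 → 47.2 | 17.8 | 67.6 → 81.4 | 13.8 |
| 7.5% v 1% | 18.8 → 31.5 | 12.7 | 43.3 → 56.2 | 12.9 |
| 5% v 0% | 7.9 → 18.0 | 10.1 | 29.5 → 47.0 | 17.5 |
| 5% v 2% | 2.7 → 6.5 | 3.8 | 7.7 → 13.6 | 5.9 |

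**Single tables at 60 per arm (Fisher p v Boschloo p).** 5 v 0: 0.057 v 0.038. 7 v 1: 0.061 v 0.042. 9 v 2: 0.053 v 0.035. All three change sides of 0.05.

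**Equivalent enrollment.** To match Boschloo at 60 per arm for 10% v 0%, 1% and 2%, Fisher needs 72, 73 and 74 per arm, which is 24 to 28 more patients in total.

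**The case against.** Fisher's test is standard for sparse tables and keeps the type I error below 5%, so nothing in the plan is invalid. That stands. A reader might infer that the SAP misstates its error rate, but 0.05 is a significance threshold, and a test that stays under it respects it. Boschloo does not spend the full 5% at low rates either.

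The protocol's wording might have led to Fisher for RAO anyway. At 10% v 2% the expected count is (6 + 1.2)/2 = 3.6 events per arm, below the customary cut-off of 5 (an assumption, since the documents set none). This is fair, but it leaves open whether a better exact test exists.

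A reader might also infer that every discrete outcome runs at 1-2%. It does not: at event rates of 20-50% Fisher's size is 2.8-3.5%. Nor is a gain of 12-17 points general for RAO. At 60 per arm it requires a control rate toward the top of the 5-10% range and a near-complete effect. The control arm documents patent hemostasis, for which the protocol quotes under 5%, and small effects gain only about 4-5 points.

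Finally, the SAP is written in the past tense and may describe finished analyses. A switch to a less conservative test after results are known would harm credibility. This objection stands and limits the fix.

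**Conclusion.** The point holds as a matter of efficiency. For RAO at 60 per arm and event rates of 5-10%, Fisher's actual size is about 1-2%. Boschloo offers the same two-sided 5% guarantee (maximum 4.9%), never loses a Fisher rejection, and gains between about 4 and 18 points of power in the scenarios shown. At 90 per arm the gain for 10% v 0-2% is about 6-9 points, although it stays larger at lower control rates with a near-complete effect.

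These sizes rest on equal arms, on the protocol's background rate applying to the control arm, and on assumed SSA rates. The conclusion does not depend on whether RAO is treated as primary or secondary, but the two protocol sections should be reconciled.

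A reader might infer that changing the test rescues the RAO objective. It does not: with Boschloo at 60 per arm, power is still 13% for 10% v 5%, 39% for 10% v 2% and 18% for 5% v 0%. The larger limitation is that the trial was not sized for RAO.

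**What to change.** In the SAP sentence on discrete data, name Boschloo's unconditional exact test (two-sided, 0.05, with the two-sided Fisher p value as ordering statistic) for the two-group yes/no outcomes: RAO at discharge or 24 hours, access-site complications, and any hematoma. Keep Fisher's test as a descriptive check on these, and for the remaining discrete data such as the four-category Barbeau patterns.

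Make the change before outcomes are seen by arm. If they have already been seen, leave Fisher as the planned test and report Boschloo only as a labelled sensitivity analysis.

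The cost is one sentence, with no patients and no new data. The test is less familiar to readers and may need a program other than the SPSS version named in the SAP. State in the code that the two arms are the two binomial samples, because a transposed table gives a different p value.
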